10.2.6. Relationship Between Outcome Variables and Smoking Cessation

This objective will explore relationships between subject-reported outcomes and smoking cessation outcomes during the study treatment period (primary efficacy endpoint), as well as smoking cessation endpoints at Week 4 (initial quit rate endpoint) and from Week 5 to Week 8 (abstinence from Week 5 to Week 8 endpoint). It is expected that the relationship between each

of these endpoints and each of the following subject-reported outcome variables will be evaluated for this objective:

- Change during the treatment period, in self-reported number of cigarettes smoked over the previous 24 hours.
- Total scores, and change from baseline scores, for the following questionnaires: HADS, SBQ-R, Tobacco Craving, and Alcohol Use.
- Adverse event outcomes such as whether the subject experienced any adverse events, any serious adverse events.
- Compliance outcomes such as percent of study drug taken, number of behavioral support sessions attended.

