12.2.3. Treatment Period

Treatment Day 1

All subjects must begin treatment on the morning of Day 1 and record all dosing in a diary.

Clinic to contact subject via telephone call in afternoon or evening of Treatment Day 1 to:

1. Verify subject is taking treatment according to their assigned dose schedule, review compliance requirements and answer any questions.
2. Verify subject is recording number of cigarettes smoked in past 24 hours in the diary (to be recorded at the same time each day).
3. Ask subject if any adverse events have occurred and/or any changes in concomitant medications.
4. Remind subject of their appointment time for the following day and that they must bring with them all study medication packs.

Treatment Day 2

1. Subject to complete the short form of the Tobacco Craving questionnaire ([Appendix 4](#)).
2. Review diary to verify dosing up to time of visit. Review number of cigarettes smoked in past 24 hours from subject's diary (e.g. Day 1).
3. Assess for AEs at time of visit and record.
4. Vital signs, including weight.
5. Review medication packs for compliance.
6. Provide subject with behavioral support information that includes counseling ([Appendix 7](#)). NOTE: it should be stressed to subjects that even if they are smoking less, they must maintain their dosing schedule throughout the Treatment Period.
7. Blood for hematology and serum chemistry testing.
8. Remind subject of their appointment time for the following day and that they must bring with them all study medication packs.

Treatment Day 3

1. Subject to complete the short form of the Tobacco Craving questionnaire ([Appendix 4](#)).
2. Review diary to verify dosing up to time of visit. Review number of cigarettes smoked in past 24 hours from subject's diary (e.g. Day 2).
3. Assess for AEs and any changes to concomitant medications at the clinic visit.
4. Vital signs, including weight.

5. Review medication packs #1 and #2 for compliance and collect pack #1 (which should be empty, as it contained medication for days 1-2). Distribute pack #3 (for Days 5-7).
6. Provide subject with behavioral support information that includes counseling ([Appendix 7](#)). NOTE: it should be stressed to subjects that even if they are smoking less during the study treatment, they must maintain their dosing schedule throughout the Treatment Period.
7. Blood for hematology and serum chemistry testing.

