4.1.1. Primary Efficacy Endpoint

The primary efficacy endpoint will be based on the daily cigarette consumption data recorded in the subject diary. The primary efficacy endpoint is defined as the percent of expected cigarettes smoked computed for each subject, at end of treatment. This percent is designated by Y, Y is calculated as below:

$$Y = \frac{100 \times N}{T \times R}$$

where N represents total number of cigarettes smoked each day over the treatment period from Day 1 to Day 25; T represents number of post-randomization days where number of cigarettes smoked is recorded; and R represents the average number of cigarettes smoked daily over the 7-day screening period as baseline. T*R represents the total number of cigarettes that would have been smoked without intervention over the number of recorded days.

If a subject has no cigarette-count data collected post-randomization, then the primary endpoint will be imputed to a value of 100 (i.e., no change from baseline cigarette consumption). This is equivalent to imputing the total number of post-randomization days with data recorded (T) is 25 and the total number of cigarettes smoked over the treatment period (N) is the average number smoked daily at baseline (R) times 25.

The primary comparisons for this endpoint will be comparisons of active arms to the associated placebo arm, refer to [Figure 1](#):

Arm A (1.5 mg cytosine commercial schedule) versus Arm C (placebo commercial schedule),
Arm B (3.0 mg cytosine commercial schedule) versus Arm C (placebo commercial schedule),
Arm D (1.5 mg cytosine tid schedule) versus Arm F (placebo tid schedule), and
Arm E (3.0 mg cytosine tid schedule) versus Arm F (placebo tid schedule).

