4.1.2. Other Efficacy Endpoints

The endpoints associated with the other efficacy objectives are:

Abstinence from Week 5 to Week 8 is a binary endpoint (success, failure). Success is defined for a subject as having reported smoking abstinence (no cigarettes since the last clinic visit and over the past 7 days) at each clinic assessment from Week 5 to Week 8 with biochemical verification at each assessment. Biochemical verification will be defined by a CO concentration in exhaled breath of less than 10 ppm. Subjects will be allowed only 1 missed visit (smoking status and/or biochemical verification status unknown) between Week 5 and Week 8 (i.e. one of Week 6 or Week 7 visits only) for analysis of the abstinence from Week 5 to Week 8 endpoint.

Any outcome other than success will be regarded as a failure. There are therefore two types of failure for subjects: (1) subjects with adequate data that they were smoking at any time from Week 5 to Week 8 (either by the subject's self-report of smoking or CO \geq 10 ppm) and (2) subjects having insufficient data to be determined as a success for abstinence from Week 5 to

Week 8 endpoint (e.g., subjects lost to follow-up, missing the Week 5 and/or Week 8 clinic visit, or missing both the Week 6 and Week 7 visits).

All subjects will have a realization of this endpoint, thereby enabling analyses that follow the intent-to-treat (ITT) principle without imputation.

Initial quit rate is a binary endpoint (success, failure) at Week 4 (Day 27 EOT). Success is defined for a subject as having reported smoking zero cigarettes in the subject diary at Day 25, with biochemical verification by an expired-air CO reading <10 ppm at the Day 27 EOT clinic visit. Any other outcome will be regarded as a failure. This endpoint is defined at the End of Treatment visit so that subjects have approximately a 2½-week grace period after the Day 5-7 quit date. All subjects will have a realization for this endpoint, thereby enabling analyses that follow the ITT principle without imputation.

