9.3. Behavioral Support Compliance

Per protocol, subjects will receive a total of 13 behavioral support sessions at visits: SV2, Day 0, Day 2, Day 3, Day 6, Day 12, Day 16, Day 20, Day 27 EOT, Week 5, Week 6, Week 7 and Week 8.

The total number of behavioural support sessions received will be calculated for each subject and summarized by treatment arm for the Safety Analysis Set. Summaries will also be provided for compliance with behavioral support [(# behavioral support sessions received) / (# behavioral support sessions planned] * 100.

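### SAP 10.2.6 relates smoking endpoints to diary-count change and to sessions attended, two variables that partly share data or failure rules with those endpoints, so some associations will arise by construction

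*SAP*

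**What the plan says.** SAP 10.2.6, repeated in SAP 4.1.2, names three endpoints for objective 4: Y, initial quit at Week 4, and abstinence from Week 5 to Week 8. It expects each of them to be related to each variable on a list. Two entries matter here: "Change during the treatment period, in self-reported number of cigarettes smoked over the previous 24 hours" and "Compliance outcomes such as percent of study drug taken, number of behavioral support sessions attended".

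The sources of the endpoints are defined elsewhere:

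- Y (SAP 4.1.1): "The primary efficacy endpoint will be based on the daily cigarette consumption data recorded in the subject diary". Protocol 12.2.3 shows that the 24-hour count is the same diary entry. On Day 1 the clinic is to "Verify subject is recording number of cigarettes smoked in past 24 hours in the diary".
- Initial quit (SAP 4.1.2): "Success is defined for a subject as having reported smoking zero cigarettes in the subject diary at Day 25", with an expired CO below 10 ppm at the Day 27 visit. Anything else is a failure.
- Week 5 to 8 abstinence (SAP 4.1.2): failure for insufficient data includes "missing the Week 5 and/or Week 8 clinic visit, or missing both the Week 6 and Week 7 visits".
- Sessions (SAP 9.3): 13 are planned, the last five at "Day 27 EOT, Week 5, Week 6, Week 7 and Week 8".

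Neither section excludes overlapping pairs, limits the time window of a predictor, defines the change in count, or names a method.

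**The concern.** An association between an endpoint and a variable is informative only if the two could have come out unrelated. For some pairs on this list they could not.

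With diary change, the endpoint is set against a summary of the same daily counts. With sessions, one missed visit can act on both sides: it lowers the session count and it forces a failure. A reader who then sees that subjects with more sessions were more often abstinent could take it for a counselling effect, although part or all of it may be the failure rule at work.

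**Working it through.** **The plan's own count.** SV2, Day 0, Days 2, 3, 6, 12, 16, 20 and 27, and Weeks 5, 6, 7 and 8 make 13 sessions, as SAP 9.3 states. Four are at the visits that decide Week 5 to 8 abstinence, and one is at the visit that decides initial quit.

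**Diary change against Y.** Y = 100 × N/(T × R). The mean count is N/T, so the mean percent change from baseline over the recorded days is 100 × (N/T − R)/R = Y − 100. The correlation is exactly 1.

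Other definitions of change were simulated with 100,000 subjects. The baseline was 16.25 (SD 3.5) cigarettes a day, from Protocol 4.1, with an assumed floor of 10. Daily counts were Poisson, and an assumed 12% or 36% quit on Days 5 to 7. The noise-only columns have no quitting: counts stay at baseline, or are halved throughout.

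| Definition of change | r with Y, 12% / 36% quit | r with Y, noise only: baseline level | r with Y, noise only: halved |
|---|---|---|---|
| Mean percent change from baseline | 1.00 / 1.00 | 1.00 | 1.00 |
| Mean absolute change from baseline | 0.90 / 0.89 | 0.98 | 0.31 |
| Day 25 minus baseline | 0.79 / 0.82 | 0.20 | 0.16 |
| Day 25 minus Day 1 | 0.59 / 0.65 | 0.00 | 0.00 (−0.005) |

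The overlap runs from identity to none under pure noise, depending on a definition the SAP does not give.

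**Diary change against initial quit.** Success needs a Day 25 count of zero. Across the four definitions the correlation with that zero was −0.43 to −0.78 when quitting was simulated.

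**Sessions against Week 5 to 8 abstinence.** Success needs Week 5, Week 8 and at least one of Weeks 6 and 7. A subject with fewer than three of the four follow-up visits therefore cannot be a success, which fixes the direction without simulation.

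For the size, 400,000 subjects were simulated. SV2 and Day 0 were always attended, later visits were missed at random with probability 3%, and a given share dropped out at a uniformly chosen later visit. True abstinence was drawn independently of attendance, and each attended visit was taken to deliver its session. The documents give no dropout rate, so dropout and miss rates are assumptions. The 12 to 36% abstinence range uses the percentages in the sample-size text (Protocol 16.3, SAP 3.5).

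| True abstinence | 5% dropout | 10% | 20% | 30% |
|---|---|---|---|---|
| 12% | 0.079 | 0.105 | 0.141 | 0.167 |
| 24% | 0.118 | 0.158 | 0.210 | 0.244 |
| 36% | 0.158 | 0.207 | 0.271 | 0.316 |

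The cells are correlations of session count with success. The correlation with true abstinence was between −0.003 and 0.004 throughout. At 24% abstinence and 10% dropout, success was 22.3% with 11 or more sessions and 0.5% with fewer. With 250 subjects, P<0.05 then occurred in 91% of trials. It occurred in 18% at 12% abstinence and 10% dropout, and in 78% at 12% and 20%.

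**Sessions against initial quit.** Day 27 is both a session and the CO visit. The same model gives r = 0.06 to 0.29.

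**Sessions against Y.** The explicit rule linking them is narrow: "If a subject has no cigarette-count data collected post-randomization, then the primary endpoint will be imputed to a value of 100". It is not pursued here.

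**What removes the artefact.**

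- Shortening the window alone is not enough. Counting sessions only through Day 20 still leaves r = 0.04 to 0.21, because early dropouts remain failures.
- Dropping only the insufficient-data failures selects on the outcome. One report of smoking is enough to classify a smoker, while an abstainer needs three visits. When the miss probability was allowed to vary between subjects, this left r of about 0.07 to 0.10 and an odds ratio of about 1.9, with no true effect.
- Restricting on attendance of the endpoint visits, whatever the outcome, gives r = 0.00. Among those subjects success equals true abstinence, which the model makes independent of attendance.

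**The case against.** The strongest reply is that little hangs on this. Objective 4 is exploratory. SAP 6.1 sets no alpha and treats P values qualitatively. SAP 10.2.6 says only that these relationships are expected to be evaluated, and the SAP's list of tables and figures names no output for them. Neither variable is among the protocol's own examples for the objective, which are anxiety, withdrawal, depression, craving and alcohol use. All of this stands, and it limits the weight of the point. It does not make the overlapping pairs informative, and the text does ask for them.

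A reader might infer more than the documents support:

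- *That the artefact would distort Phase 3 planning.* Protocol 5 ties Phase 3 sample size to results obtained under the planned behavioral support. It does not use an association between attendance and abstinence, and all arms receive the same support.
- *That every initial-quit success has a change of exactly −100%.* That is so only if change means baseline to Day 25, which the SAP does not say.
- *That diary change is useless throughout.* For Week 5 to 8 abstinence it precedes the outcome and is a legitimate predictor.
- *That one odds ratio measures the sessions artefact.* With 30% abstinence, 5% sporadic misses and 10, 20 and 30% dropout, a cut at 12 sessions gives about 3.9, 6.5 and 9.7. A cut at 11 gives about 19, 39 and 64. With 10% sporadic misses, the cut at 12 gives about 2.5, 3.4 and 4.5. The SAP sets no cut.

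**Conclusion.** The point holds for four pairs: diary change with Y, diary change with initial quit, sessions with initial quit, and sessions with Week 5 to 8 abstinence. The first ranges from an identity to no built-in correlation under pure noise, depending on how change is defined. The sessions pairs carry a positive association made by the failure rules: about 0.1 to 0.3 for both endpoints, under the assumed dropout, miss and abstinence rates.

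The primary comparisons and the abstinence comparisons between arms are unaffected. The questionnaire and adverse-event variables are not built from smoking data, and percent of study drug taken comes from dosing entries, so those parts of the objective stand. The consequence is a possible misreading of one exploratory analysis, chiefly of counselling attendance as a cause of abstinence. It is worth correcting because the correction is nearly free.

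**What to change.** In SAP 4.1.2 and 10.2.6:

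1. Delete change in the diary cigarette count as an explanatory variable for Y and for initial quit. Keep it only for Week 5 to 8 abstinence, and define the change.
2. For Week 5 to 8 abstinence, count only sessions through Day 27 EOT. Restrict the sessions analysis, regardless of outcome, to subjects who attended Week 5, Week 8 and at least one of Weeks 6 and 7 with smoking and CO status known.
3. For initial quit, count only sessions through Day 20, among subjects with a Day 25 diary entry and a Day 27 CO reading.

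This is SAP wording only, with no new data. The cost is fewer subjects in an exploratory association, which then applies only to those who attended the endpoint visits; the report should say so. The restriction removes the association made by the failure rules. It does not remove selection if staying in the study itself depends on smoking.

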10.2.7. Relationship Between Outcome Variables and Nicotine Metabolite Ratio (NMR)

The correlation of NMR with reduction in cigarette use (primary efficacy endpoint), initial quit rate and abstinence from Week 5 to Week 8 will be explored. Descriptive statistics for NMR, reduction in cigarette use and the cessation endpoints will be produced.

10.2.8. Questionnaires

The HADS, SBQ-R, Tobacco Craving and Alcohol Use questionnaires will be administered at [Section 8.6](#).

The HADS, SBQ-R and Tobacco Craving questionnaires will be summarized using descriptive statistics. For each questionnaire score, the actual value, change from baseline and percent change from baseline will be summarized by treatment arm and visit. Only subjects with non-missing results at both baseline and the post-baseline visit will be summarized at each time point.

The individual items on the Alcohol Use questionnaire will be summarized categorically by treatment arm and visit.

11. SAFETY ANALYSIS

All safety analyses described below will be presented for each treatment arm using the Safety Analysis Set defined in [Section 6.4](#). No statistical comparisons between treatment arms are planned for safety endpoints; thus, no statistical test results will be reported.

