6.3. Safety Objectives

1. To evaluate overall safety profiles of cytisine when administered at 1.5 mg or 3.0 mg, using the 25-day commercial titration or simplified tid schedules, compared to placebo.

[figure not shown]

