3.3. Safety Objective(s)

To evaluate overall safety profiles of cytisine when administered at 1.5 mg or 3.0 mg, using the commercial 25-day titration or simplified tid schedules, compared to placebo.

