6. DATA ANALYSIS CONSIDERATIONS

6.1. General Considerations

The overall goal of the study is to obtain estimates of effect size for efficacy and safety endpoints that will be used to inform the design of future studies. As stated in the protocol, this study will be analyzed without specific statistical criteria. That is, no formal statistical hypothesis testing will be conducted and consequently a level of significance (α level) is not specified in this Statistical Analysis Plan. There will be statistical testing with P values and confidence intervals computed. The P values will be interpreted as an assessment of consistency with the play of chance (small P values indicating a small likelihood the observed effect is due to chance) and will be used qualitatively in decisions concerning next steps.

Statistical analyses will be performed at the conclusion of the study once all data have been collected, cleaned, and the database has been locked.

Medical history events and adverse events will be coded to standard “preferred terms” and “system organ classifications (SOC)” using the Medical Dictionary for Regulatory Activities (MedDRA) Version 21.0.

Concomitant medications will be coded using the World Health Organization Drug Dictionary (WHODRUG) Version Sep-2017 B2.

All statistical programming will be done using SAS[®] version 9.4 (SAS[®] Institute, Cary, North Carolina). All tables, figures and listings will be produced in landscape format.

In general, all data will be listed by treatment arm, subject and visit/time point where appropriate. The summary tables will have columns corresponding to, or be stratified by, treatment arm. The 6 treatment arms are: 1.5 mg Cytisine – Commercial Schedule, 3.0 mg Cytisine – Commercial Schedule, Placebo – Commercial Schedule and 1.5 mg Cytisine – tid Schedule, 3.0 mg Cytisine – tid Schedule, Placebo – tid Schedule.

The total number of subjects under the stated analysis set in each treatment arm (N) will be displayed in the header of summary tables.

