6.5. Key Study Endpoints

Achieve has identified the following endpoints as key study endpoints:

- Percent of expected cigarettes smoked (primary efficacy endpoint, see [Section 4.1.1](#))
- Abstinence from Week 5 to Week 8 (other efficacy endpoint, see [Section 4.1.2](#))
- Adverse events (serious adverse events, adverse events that resulted in dose reduction or discontinuation of study drug, all adverse events)

- Exposure to study drug, including study drug compliance

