11.1. Adverse Events

Per the study protocol all adverse events (AE) occurring during the study, whether or not attributable to study drug, will be recorded in the subject's source documents and CRF. Adverse event reporting will start at the date of informed consent and continue through the end of study (Week 8 visit).

AE severity will be assessed by the Investigator as mild, moderate or severe. The Investigator will also assess the relationship of each AE to study drug (none, unlikely, possible, probable, definite). Treatment-related AEs are defined as events the Investigator considers to be possibly, probably, or definitely related to study drug, as well as events with “unknown” relationship.

Adverse event summaries will present data by treatment arm.

An overall summary of adverse events will be provided that reports, for each treatment arm, both the number (%) of events meeting a specific criterion and the number (%) of subjects with at least one event meeting that criterion. Events meeting the following specific criteria will be presented in this table:

- Any reported adverse event (i.e., both pre-existing and treatment-emergent events)
- For treatment-emergent AEs:
 - Any TEAE
 - Any serious TEAE
 - TEAEs by severity (mild, moderate, severe)
 - TEAEs by relationship (none, unlikely, possible, probable, definite)
 - TEAEs by relationship (not related, related)
 - TEAEs by action taken with study drug (dose increased, dose not changed, dose reduced, dose interrupted, drug withdrawn, not applicable, unknown)
 - TEAEs by outcome (recovered no sequelae, recovered with sequelae, ongoing, death)

In addition to the overall summary, the following summaries of the number (%) of subjects with at least one TEAE will be produced:

- Incidence by SOC and PT, in alphabetical order of SOC and PT, for both all TEAE and related TEAE
- Incidence by PT, in decreasing frequency of PT, for both all TEAE and related TEAE
- Incidence of TEAEs that resulted in dose reduction or discontinuation of study drug (i.e., action taken with study drug reported as dose reduced, dose interrupted, or drug withdrawn), in decreasing frequency of PT
- Incidence of TEAE by PT and severity (mild, moderate, severe), in alphabetical order of SOC and PT
- Incidence of TEAE by PT and relationship (yes, no), in alphabetical order of SOC and PT

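### The SAP's goal and safety objective call for between-arm safety estimates, but its safety section rules out between-arm comparisons and plans no safety effect measure or interval

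*SAP*

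**What the plan says.** - **Goal.** SAP 6.1: "The overall goal of the study is to obtain estimates of effect size for efficacy and safety endpoints", for use in designing later studies.
- **Safety objective.** Protocol 6.3 evaluates the safety of the two doses "using the 25-day commercial titration or simplified tid schedules, compared to placebo"; SAP 3.3 has the same objective, "using the commercial 25-day titration or simplified tid schedules, compared to placebo".
- **Key endpoints.** SAP 6.5 includes "Adverse events (serious adverse events, adverse events that resulted in dose reduction or discontinuation of study drug, all adverse events").
- **Inference.** SAP 6.1 says that "no formal statistical hypothesis testing will be conducted" and sets no alpha level, but adds: "There will be statistical testing with P values and confidence intervals computed". That second sentence is not limited to efficacy.
- **Safety analysis.** SAP 11: "No statistical comparisons between treatment arms are planned for safety endpoints; thus, no statistical test results will be reported".
- **Planned safety output.** SAP 11.1: "Adverse event summaries will present data by treatment arm". Sections 11.1 to 11.7 list counts and percentages of adverse events, a Kaplan-Meier figure of time to first treatment-emergent adverse event (TEAE), laboratory and vital-sign values with change from baseline, laboratory shift tables, potentially clinically significant vital signs, ECG shifts and concomitant medications. All are by arm.

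**The concern.** The general section promises effect sizes for safety, the objective is comparative, and the operative section excludes the comparison. A programmer who follows SAP 11 exactly will produce no between-arm safety measure and no interval.

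Protocol Section 5 and the synopsis say that the trial evaluates dose and schedule and that safety profiles are to be compared with the respective placebo arms. Protocol 7.3.1 justifies a separate placebo for each schedule partly so that adverse event reporting can be properly assessed. Without a planned contrast, readers will compare percentages by eye across arms of 50 and 25. A similar-looking pair of percentages may then be taken as evidence of no excess risk, although the data could not exclude a sizeable one.

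**Working it through.** **Does any section plan a between-arm safety estimate?**

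| Item | Efficacy | Safety |
|---|---|---|
| Named in the effect-size goal (SAP 6.1) | Yes | Yes |
| Objective framed against placebo | Yes (SAP 3.1, 3.2) | Yes (SAP 3.3) |
| Between-arm measure | LS mean differences (10.1.1); common odds ratios (10.2.1, 10.2.3, 10.2.4) | None named |
| Interval on that measure | 95% CIs (10.1.1); forest plots of 95% CIs for odds ratios (10.2) | None named |

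The general sentence on P values and intervals in SAP 6.1 does not fill the gap. SAP 11 is the specific rule for safety and excludes comparisons. The table shells in SAP Section 15 are redacted, but the statement in SAP 11 is explicit.

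**The plan's own precision figure.** SAP 3.5 gives a half-width of 8.3 for a primary between-arm difference, from SD 17 and arms of 50 and 25:

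t(0.975, 73 df) × 17 × √(1/50 + 1/25) = 1.993 × 4.164 = 8.30.

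It reproduces. No precision figure is given for a safety endpoint.

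**What safety intervals would look like.** The documents give no TEAE rates for this design, so the counts below are assumptions; the arm sizes are from Protocol 7.4. The method is the Newcombe interval. With Wilson 95% limits (l, u) for each arm and d = p₁ − p₂:

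- lower = d − √[(p₁ − l₁)² + (u₂ − p₂)²]
- upper = d + √[(u₁ − p₁)² + (p₂ − l₂)²]

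Example, 12/50 against 3/25: p₁ = 0.240 (0.143, 0.374), p₂ = 0.120 (0.042, 0.300), d = 0.120.

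- lower = 0.120 − √(0.097² + 0.180²) = −0.084
- upper = 0.120 + √(0.134² + 0.078²) = 0.275

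| Assumed counts | Difference (points) | 95% CI |
|---|---|---|
| 5/50 vs 1/25 | +6.0 | −10.5 to 17.8 |
| 12/50 vs 3/25 | +12.0 | −8.4 to 27.5 |
| 30/50 vs 10/25 | +20.0 | −3.7 to 40.7 |
| 32/50 vs 16/25 | 0.0 | −21.0 to 22.8 |
| 12/50 vs 6/50 | +12.0 | −3.3 to 26.9 |
| 30/50 vs 20/50 | +20.0 | 0.5 to 37.5 |

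The first four rows have the sizes of an active arm against its own placebo; their widths run from about 28 points (17.8 + 10.5) to 44 (40.7 + 3.7). The last two have the sizes of one dose against the other within a schedule, or of one active arm against pooled placebo.

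**Zero events.** The exact two-sided 95% upper limit is 1 − 0.025^(1/n): 13.7% for n = 25 and 7.1% for n = 50.

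**The case against.** The best defence is that SAP 11 follows the protocol. Protocol 16.4 says that safety data are primarily assessed clinically and summarised for each treatment, and the goal in Protocol 16.1 does not mention safety. Description beside a concurrent placebo column is a common way to serve a comparative safety objective in Phase 2b, and a crude difference can be derived from the by-arm counts. On this view the only firm conflict is the mention of safety in SAP 6.1, and deleting it would restore consistency.

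Part of this stands. The absence of safety tests is consistent with the study's stance and is not a fault. But efficacy is under the same stance and still receives differences and odds ratios with intervals; an interval needs no test. Deleting safety from the goal would remove the contradiction with SAP 6.1, but the comparative objective would still have no planned estimate.

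Three stronger readings are tempting but unsupported:

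- *That the trial will yield no safety estimates.* By-arm incidences, mean changes and Kaplan-Meier curves are planned. Only the between-arm measure and its interval are missing.
- *That the trial selects the Phase 3 dose, so the omission undermines that choice.* The documents say that it evaluates doses and schedules and informs Phase 3 design and sample size. They contain no selection rule.
- *That ACH-CYT-02 shows what the intervals would reveal.* Its moderate-event rates, 41.7% and 16.7%, come from the 3.0 mg and 1.5 mg groups of an open-label study with 12 subjects each and no placebo. Neither is a placebo rate.

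**Conclusion.** The concern holds as an internal inconsistency with a practical consequence: SAP 6.1 and the safety objective call for between-arm safety estimates, and SAP 11 excludes them. It should be corrected, but its importance is moderate, because it does not touch the primary efficacy analysis and the underlying counts will be reported.

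Adding intervals will not make the safety comparison decisive. Against a 25-subject placebo arm, all four assumed scenarios include zero. Their value is to show how little the by-arm percentages can exclude: equal observed rates of 64% remain compatible with an excess of more than 20 points. These sizes rest on assumed counts and on the planned arm sizes being reached.

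**What to change.** Replace the sentence in SAP 11 with:

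> No hypothesis tests or P values will be reported for safety. For any TEAE, moderate-or-severe TEAE, related TEAE, SAE, TEAE leading to dose reduction or discontinuation (as defined in Section 11.1), and the most frequent preferred terms, the risk difference with 95% CI (Newcombe) will be reported within schedule for A vs C, B vs C, D vs F and E vs F, and for 3.0 mg vs 1.5 mg (B vs A, E vs D). These are descriptive and unadjusted for multiplicity.

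The frequency cut-off for preferred terms should be fixed before unblinding.

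Pooled placebo should be supplementary only, under the condition that SAP 10.1.2 and 10.2.2 already set for efficacy, that the placebo arms are similar. A dose should not be pooled across schedules as a main analysis, because exposures differ: Protocol Tables 8 and 9 give 18 mg against 9 mg per day on Days 1 to 3 for the 3.0 mg dose, and SAP 9.2 gives 100 against 69 doses overall.

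If the sponsor prefers purely descriptive safety reporting, the minimum is to remove safety from the effect-size goal in SAP 6.1 and to say how the comparison with placebo will be made.

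The cost is SAP wording and one table or forest plot, using data already collected. The downside is several wide, unadjusted intervals, which must be labelled as such.
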